3.1.3. Independent Data Monitoring Committee

An Independent Data Monitoring Committee (IDMC) will be set up during the study. In the phase Ib, the IDMC will be composed of 2 independent clinicians, external to the study.

In the phase II part 2, the IDMC will be composed of 2 independent clinicians and 1 independent statistician.

Representatives of Transgene (Medical monitor, Clinical Project Manager, Pharmacovigilance physician) and Merck KGaA / EMD Serono (Medical monitor) will be invited to all meetings for reporting of clinical data and to respond to any specific questions the IDMC may have on the conduct of the study.

Additional study team members may attend if deemed necessary (Clinical trial manager, Statistician). If deemed appropriate, the coordinating investigator of the study and the study investigators of the concerned centers will be invited for cases requiring specific explanation. The Sponsor can appoint any additional independent expert if needed.

A charter describing the responsibilities of the IDMC as well as the working procedures will be provided in a separate document.

- *In the phase Ib of the study:*

During the phase Ib of the study, the safety data of all enrolled and treated patients will be collected and evaluated by the Investigators, Transgene and Merck KGaA / EMD Serono on an ongoing basis. The IDMC will meet before each new cohort begins to analyze and review the safety data of all patients in the previous cohort. The IDMC will then recommend on continuation of accrual and whether it is possible to do the dose escalation as per the study design.

At the end of the phase Ib and depending on the nature of the toxicities observed, the safety data of all patients will be analyzed and discussed with the IDMC which will make recommendation to the sponsor on the start of accrual in the phase II of the study. DLT evaluation is performed 4 weeks after the last patient enrolled in the phase Ib had first dose of study treatments.

- *In the phase II part 1 of the study:*

During the phase II part 1 of the study the IDMC will review safety data at interim analysis. However, the IDMC may meet at any time on Sponsor request, especially in the case of unexpected toxicities or significant SAEs occurrence.

- *In the phase II part 2 of the study:*

During the phase II part 2 of the study and in addition to safety review the IDMC will evaluate efficacy results at interim analysis.

3.1.4. Patient accrual and duration of study

This study is expected to start in Q3 2017 and is expected to be completed by Q4 2024. For safety reasons, inclusion of the patients in the phase Ib will be performed with a security interval of 2 weeks between the first patient of each cohort and the next 2 patients of the cohort.

In case of no safety concerns and for the further conduct of the study it is understood that the accrual rate is based on reasonable planning expectations. The actual accrual rate should be compared to the expected rate on an ongoing basis. If problems with recruitment are encountered this should be discussed with Transgene as early as possible in order to institute measures to meet the above timelines.

3.2. Discussion of study design

The study is designed as a phase Ib/II trial to evaluate the safety and efficacy of the combination of TG4001 with avelumab in patients with HPV-16 positive recurrent or metastatic cancer including oropharyngeal SCCHN patients.

The phase II consists of two parts: the phase II part 1 is a single arm study (TG4001 with avelumab) and the phase II part 2 is a randomized, open-label, controlled two arms study (TG4001 with avelumab vs avelumab alone).

TG4001 was studied in several clinical trials including patients with HPV-16 positive CIN2-3, HPV-16 positive cervical cancer and HPV-16 positive VIN3 at doses ranging from 5×10^5 PFU to 5×10^7 PFU administered by SC injections. The clinical data generated in CIN demonstrated that such HPV targeted active immunotherapy could eradicate HPV infected cervical cells by generating T-cell responses. In addition TG4001 displayed a good safety profile across all these studies (see Section 1.2.1).

Taking into account the fact that TG4001 has not been investigated previously in combination with avelumab, the study will be run in its first phase Ib in cohorts of 3 to 6 patients using a traditional 3+3 design to test two doses of TG4001 (5×10^6 and 5×10^7 PFU) in combination with a fixed dose of avelumab (10 mg/kg) in order to evaluate the safety profile of the combination of the two agents.

Should the data from this phase Ib of the study confirm the good tolerance of the combination, the study will be expanded (phase II of the study) to determine the efficacy of the combination in terms of overall response rate in this population of patients.

The phase II part 1 of the study is designed as an open label, single arm study evaluating the efficacy of combination of TG4001 + avelumab. The primary efficacy endpoint for the phase II of the study is ORR, this endpoint is widely accepted as directly attributable to drug effect without necessity of a control arm. It is also considered as an early endpoint allowing decision making to continue clinical development of TG4001 in combination with checkpoint inhibitors.

The phase II part 2 of the study is designed as a randomized, open label, controlled two arms study comparing the PFS of TG4001 in combination with avelumab vs avelumab alone. For the cohort of patients without liver metastases at baseline, due to the uncertainty on the true treatment effect and data variability, and to reduce the risk of running an underpowered study, it is considered appropriate to adopt an adaptive approach to the sample. This will offer a mechanism to adjust the sample size to updated treatment effect and variability estimates seen at a planned interim analysis (Mehta C.R. and Pocock S.J., 2011).

The hypothesis for median PFS in the combination arm (TG4001 with avelumab) is set at 4.5 months and the hypothesis for median PFS in the monotreatment arm (avelumab alone) is set at 2.0 months. Interim analysis is performed after 37 PFS events and based on the conditional power observed, 120 patients should be enrolled to reach at Final Analysis a conditional power of 90% based on 104 PFS. To stick with initial timelines and with an observed enrollment of only 2 patients per month, Final Analysis will be performed based on at least 69 PFS events reaching a conditional power higher than 75% corresponding to at least 80 randomized patients.

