With an one-sided type I error α at 5%, 76 events are needed to reach a power of 95%. This should happen after around 80 patients enrolled (40 patients per arm). Assuming 5% drop-out in each arm, 84 patients will be randomized.

[figure not shown]
Due to the uncertainty on the true treatment effect and data variability, and to reduce the risk of running an underpowered study, it is considered appropriate to adopt an adaptive approach for the sample size. This will offer a mechanism to adjust the sample size in response to treatment effect and variability estimates seen at a planned interim analysis.

The interim analysis will be conducted after 37 events which will occur approximately 16 months after the inclusion of the first patient. At that time, it is estimated to have around 50 patients enrolled. Based on the results of the interim analysis, sample size re-estimation will be performed. According to simulations on CHW (Cui, Hung and Wand) approach using EAST 6.5., the proposal is as follows:

- Start with a fixed sample size calculation based on the primary endpoint.
- Based on the interim analysis result maintain or increase the sample size in order to obtain the desired power of 90%.

Conditional power will be calculated based on the interim results. Should the conditional power be in the favorable or unfavorable range the sample size and the number of events will not be adjusted and will remain at the initial sample size. Conditional power falling into the promising zone will have a sample and events increase. The regions and their implications on sample size are detailed below:

- **Favorable:** If the interim results are sufficiently favorable corresponding to a CP of more than 90%, final analysis will be performed on 74 PFS events corresponding to an estimated sample size of 80 evaluable patients. This will occur approximately 26 months after the inclusion of the first patient.
- **Promising zone:** If the interim results are equivalent to a CP between 90% and 30%, the sample size will be recalculated according to the median PFS observed in the two arms with a cap of 2 times the initial events.
- **Unfavorable zone:** If the interim results are not favorable corresponding to a CP between 30% and 10%, the trial may continue up to the initial sample size of 80 patients or could be stopped
- **Futility:** If the interim results are futile corresponding to a CP lower than 10%, the trial will be stopped for futility at the interim analysis.

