Assuming an uniform enrollment with 3 patients per month and based on simulations, in case of sample size reassessment, an average of 124 events would be needed (corresponding to 136 patients). Assuming a 5% lost to follow-up or withdrawal of consent rate, a total of 142 patients should be randomized to the 2 treatment arms in a 1:1 ratio (71 patients in each treatment arm). Based on the aforementioned assumptions, a power of 70% is expected using an unstratified log-rank test at a 1-sided cumulative 5% level of significance. [REDACTED]

[REDACTED]

[REDACTED]

[REDACTED]

[REDACTED]

Full details of the adaptive method for sample size specified above will be given in the Statistical Analysis Plan (SAP).

Patients with liver metastases at baseline:

A sample size of [REDACTED] is planned.

[REDACTED]

[REDACTED]

[REDACTED]

[REDACTED]

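### Section 3.2 leaves the final PFS analysis open-ended at 69 or more events, and the visible adaptation rule in 10.2 and the synopsis does not allow for it

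*Combined protocol and SAP*

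**What the plan says.** Section 3.2 describes what followed the interim at 37 PFS events. The re-estimation gave 104 events and 120 patients for 90% conditional power. Because accrual was only 2 patients per month and the original timelines were to be kept, the "Final Analysis will be performed based on at least 69 PFS events reaching a conditional power higher than 75" per cent, corresponding to at least 80 randomized patients.

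Section 10.2 carries the adaptation rule. It says "Based on the interim analysis result maintain or increase the sample size in order to obtain the desired power of 90" per cent. In the favorable zone (conditional power above 90%) the "final analysis will be performed on 74 PFS events corresponding to an estimated sample size of 80 evaluable patients". For 30-90% it says "Conditional power falling into the promising zone will have a sample and events increase", capped at twice the initial events. The same section states that "76 events are needed to reach a power of 95" per cent. The synopsis repeats the 74-event rule, the promising zone and the cap. Neither place mentions 69 or 104 events in its visible text.

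Section 3.1.2 gives both 120 patients and at least 80 patients, each to be recruited until Q1 2024. Section 3.1.4 expects completion by Q4 2024. Section 10.4.2 names an unstratified log-rank test at the one-sided 5% level as the primary test, while 10.2 and the synopsis name the Cui-Hung-Wang (CHW) approach for the adaptation. Section 10.2 adds: "Full details of the adaptive method for sample size specified above will be given in the Statistical Analysis Plan (SAP").

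**The concern.** The time of the primary test should be fixed by something other than the accumulating comparison. Here the only visible trigger is a floor. Q1 2024 is a recruitment horizon and Q4 2024 an expected completion; neither is a data cut-off. The trial is open-label and progression is assessed locally, so information by arm is not shielded by design.

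The visible rule also points the other way. If the interim fell in the promising zone, 10.2 calls for more events than initially planned, whereas 3.2 allows fewer than 74 or 76. A reader cannot tell which event number governs, or which test statistic the quoted conditional power belongs to. At stake is whether the one-sided 5% level can be shown to hold for the primary result.

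**Working it through.** **Inputs.** Medians 4.5 and 2.0 months, one-sided 5%, power 95% (synopsis); 37 interim events, 74 and 76 initial events (10.2); 104 events for 90% conditional power and the floor of 69 (3.2). The interim z is not stated and is inferred below.

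**Initial design reproduced.** Hazard ratio = 2/4.5 = 0.444. Freedman: events = [(1.645 + 1.645) × (1 + 0.444)/(1 − 0.444)]² = (3.29 × 2.6)² ≈ 73.2, so 74. This matches the favorable-zone figure and is close to 76.

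**Power at exactly 69 events.**
- Freedman: Φ(√69 × 0.3846 − 1.645) = Φ(1.55) = 93.9%.
- Schoenfeld: Φ(√69/2 × 0.811 − 1.645) = Φ(1.72) = 95.8%.

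**Level with a fixed count.** Taking 69 events in the promising zone and 74 otherwise, with non-binding futility, integration over the interim z gives 5.04% for the unweighted log-rank and 5.00% for CHW.

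**Where the interim fell.** Assume conditional power is computed under the observed trend, with z₁ the interim statistic and D the final number of events:
- Unweighted: CP(D) = Φ[(z₁D/√37 − 1.645√D)/√(D − 37)].
- CHW with planned events N: CP(D) = Φ[z₁√((D − 37)/37) − (1.645 − w₁z₁)/w₂], with w₁ = √(37/N) and w₂ = √(1 − 37/N).

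Setting CP(104) = 90% gives:

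| Statistic | z₁ | CP at 69 | CP at 74 |
|---|---|---|---|
| Unweighted | 1.595 | 78.3% | 80.6% |
| CHW, N = 74 | 1.538 | 74.0% | 77.3% |
| CHW, N = 76 | 1.542 | 73.9% | 77.3% |

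Example, unweighted at 69: (1.595 × 69/6.083 − 1.645 × 8.307)/√32 ≈ 0.78, and Φ(0.78) ≈ 78.3%.

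Conditional power of 30% and 90% at 74 events corresponds to z₁ of 0.90 and 1.80. An inferred z₁ of 1.54-1.60 is therefore inside the promising zone.

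**What an open end could allow (illustration only).** Trials simulated under the null, tested at 1.645 after every event, counted as rejected if any cut in the range crosses:

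| Range of events | One-sided level |
|---|---|
| 69 only | 5.0% |
| 69-74 | 6.7% |
| 69-76 | 7.1% |
| 69-104 | 10.8% |

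These are for the unweighted statistic. CHW weights give practically the same values for 69-74 and 69-76, because CHW protects against the interim-based change and not against a cut chosen on later results. The 76 is 0.95 × 80, the events available with exactly 80 patients and 5% loss. Since 3.2 says at least 80, it is not a ceiling.

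**The case against.** Section 3.2 explains its departure: the re-estimation gave 104 events, accrual was slow, and the timeline was kept. Section 10.2 can be read as the rule before the interim and 3.2 as what followed from it. Patient numbers do not fall below the initial 80, and the recruitment and completion dates bound the timing loosely. That explains the change, but it neither fixes the analysis time nor amends the rule.

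Redaction is a serious limit. Lines are blacked out in the synopsis (number of patients and sample size), in 10.2 beside the sample-size text, and in 10.4.2 directly after the primary log-rank sentence. The trigger or the CHW weights may stand there or in the SAP.

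Three stronger readings are tempting and are not supported:
- **That 69 events itself damages the trial.** The level and design power above show that it does not.
- **That the cut will be chosen on results.** No passage says so, and the only efficacy review described before the final analysis is the IDMC's at the interim.
- **That the conditional power above 75% is wrong.** On the log-rank test named in 10.4.2 the back-solved figure is 78.3%. The CHW figure is about one point short, on an inferred z.

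**Conclusion.** The point holds as a defect of definition that should be fixed. The visible text gives the primary analysis a floor and no fixed time, and the visible rule in 10.2 and the synopsis is not reconciled with that floor. Placing the interim in the promising zone assumes current-trend conditional power and an inferred z of about 1.54-1.60. The possible inflation, from about 6.7% to 10.8% depending on the range, shows why a fixed trigger matters; it is neither a forecast nor a bound. The conclusion would change if a redacted line or the SAP already states a single trigger, although 10.2 would still need to agree with 3.2.

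Two minor clean-ups do not add to the weight. First, in 10.2 "Based on the aforementioned assumptions, a power of 70% is expected using an unstratified log-rank test" with an average of 124 events, yet the visible medians give 99.6-99.8% at 124; redacted lines follow, so a different effect size may have been assumed. Second, the synopsis gives two interim significance levels, 0.00001 and 0.000001, with no practical effect on the overall level.

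**What to change.** - Before the final data cut, and without reference to results by arm, state one trigger: a fixed event number or a fixed calendar cut-off date. Carry it into the synopsis, 3.1.2, 3.2 and 10.2.
- Mark as superseded the 74, 76, 104 and 124 event figures and the matching patient numbers, including the one in the sentence "Assuming a 5% lost to follow-up or withdrawal of consent rate, a total of 142 patients should be randomized to the 2 treatment arms".
- State in 10.4.2 whether the final test is the CHW statistic, with the weights fixed before the interim, or the unweighted log-rank. Do not set new weights now.
- Recompute the quoted conditional power from the actual interim data, at the chosen trigger and with that statistic.
- As minor items, state the effect size behind the 70% power and give a single interim significance level.

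The cost is wording in the protocol and SAP, some loss of flexibility in timing, and possibly a slightly lower quoted conditional power (about 74% instead of about 78% at 69 events if CHW is used, on the back-solved z).

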3.3. Doses and schedule selection

3.3.1. TG4001 doses selection

The doses of TG4001 for the Phase Ib of the study were selected based on an evaluation of the toxicology data, *in-vivo* efficacy in oncology models, and clinical data in patients with cancer treated with TG4001. TG4001 was demonstrated to be safe up to the highest dose of 5×10^7 PFU in patients with gynaecological cancers. The starting dose chosen for TG4001 will be 5×10^6 PFU, in case no DLT occurs in combination with avelumab 10 mg/kg, the dose of 5×10^7 PFU used in previous clinical trials, which demonstrated to be safe will be tested in combination with avelumab 10 mg/kg. It is expected that the combination will be safe. Nevertheless, should DLTs or unexpected toxicities occur with the combination of TG4001 and avelumab, alternative dosing regimen of TG4001 and/or avelumab will be considered (See Section 3.1.1).

3.3.2. TG4001 schedule selection

TG4001 previous clinical development in gynaecological conditions was conducted according to a standard immunization regimen of 3 injections weekly (Days 1, 8, 15). The large and most recent phase II study (study NV25025) showed TG4001 activity when compared with placebo in both histologic assessments and viral clearance, even though primary efficacy endpoint for the treatment response rate of at least 60% was not achieved. One hypothesis that may explain a lower than expected response rate is that additional administrations were needed. Indeed, other large randomised phase II studies with MVA-based products developed by Transgene [i.e. TG4010 (MVA-MUC1-IL2) and TG4040 (MVA-HCV)] completed positively with schedules of immunization characterized by more administrations (weekly for 6 weeks followed by repeated boost of vaccination at regular interval).

Both animal toxicology data from TG4001 and similar viral vectored products (TG4040 and TG4010) demonstrated an acceptable safety profile of MVA-based products. The dose, the total number of injections and the intended treatment period in the proposed study with TG4001 were tested with either TG4001 or a similar construct in 3 animal species as shown in Table 3-1 below. None of these studies evidenced toxic findings up to 20 injections for 5 months other than inflammation at the injection site.

Table 3-1 : Summary of toxicology data supportive of the intended treatment regimen

Study	Number of injections	Treatment duration	Highest dose
TG4001 / Rat	8	1 month	6×10^6 PFU
TG4001 / Mice	4	1 month	4×10^7 PFU
TG4001 / Rabbit	3	1 month	5×10^6 PFU
TG4010 / Mice	9	3 months	4×10^7 PFU
TG4040 / Rabbit	20	5 months	1×10^8 PFU

The good tolerance in animals was further confirmed in patients. Previous human experience with TG4001 and similar products is summarized in **Table 3-2**. After iterative injections with MVA-based products for several months in cancer patients or chronic hepatitis C patients, the safety profile of the recombinant vector was satisfactory; the adverse events were mainly associated to the disease or the concomitant treatment.

Table 3-2 : Previous human experience with TG4001 and similar MVA-based products

Product	Number of treated patients*	Max number of injections	Highest dose (PFU)	Summary of adverse drug reactions
TG4001 (MVA-HPV-IL2)	313	3 (weekly)	5×10^7	injection site reactions, including erythema, pain, or reaction not otherwise specified
TG4010 (MVA-MUC1-IL2)	380	51 (weekly for the first 6 weeks then every 3 weeks up to progression)	1×10^8	fatigue, injection site reactions, erythema
TG4040 (MVA-HCV)	173	13 (weekly)	1×10^8	injection site reactions, fatigue, flu-like symptoms, headache

*as of December 2016

Based on the safety review from available animal and clinical studies conducted with our MVA-based products injected dozens of times per individual, there is no known toxicity after multiple administrations of MVA viruses. Thus, the company believes that the dose regimen of TG4001 in the proposed study is safe.

Therapeutic vaccines do not directly target the tumor but they rather aim to activate and amplify the immune reactions against the tumor. Immune responses often take time to develop and can potentially be enhanced by continued booster vaccinations. Therefore, the proposed schedule of administration of TG4001 in co-administration with avelumab in the present study uses weekly SC injections of TG4001 on Days 1, 8, 15, 22, and 29 of study treatment, then once every 2 weeks (starting on Day 36) up to Month 6, thereafter once every 12 weeks up to Month 24, fitting with the schedules of administration of the two other MVA based products and with the schedule of visits at the hospital.

3.3.3. Avelumab dose selection

The avelumab dose of 10 mg/kg was selected after review of the PK, pharmacodynamics, receptor occupancy, and preliminary clinical safety and efficacy data observed in the ongoing Phase I to III monotherapy studies of over 1700 subjects that have received this dose.

For the phase II part 2 avelumab will be administered at 800 mg flat dose every 2 weeks at the same schedule as in phase Ib and phase II part 1. This dose regimen has been approved in global markets. Avelumab was originally dosed on a mg/kg basis to reduce inter subject variability in drug exposure. However, data for mAbs, including the marketed PD-1 and PD-L1 ICIs inhibitors nivolumab, pembrolizumab and atezolizumab, reveal that body weight based dose regimens do not result in less variability in measures of exposure over fixed (i.e., body weight independent) dose regimens (Wang D.D. *et al.*, 2009), (Freshwater T. *et al.*, 2017), (Zhao X. *et al.*, 2017). Simulation showed that exposures to avelumab across the available range of body weights are less variable with 800 mg every 2 weeks compared with 10 mg/kg every 2 weeks; exposures were similar near the population median weight. Furthermore, the 800 mg every 2 weeks dose regimen is expected to result in $C_{trough} > 1 \text{ mg/mL}$ required to maintain avelumab serum concentrations at > 95% TO throughout the entire every 2 weeks dosing interval in all weight categories. Furthermore, the advantages of flat dosing are minimizing drug wastage, facilitating preparation and administration, and reducing pharmacy errors (Wang D.D. *et al.*, 2009).

